6.2 Treatment of Outliers

Individual concentration-time points, if considered anomalous, may be excluded from the analysis at the discretion of the pharmacokineticist following a review of the available documentation. Any such exclusion will be discussed with the sponsor and clearly outlined in the study report.

Entire individual treatment profiles for a participant may be excluded following review of the available documentation and discussion with the sponsor. However, results of analysis with and without the excluded profiles may be presented in the study report. Any such exclusion will be clearly listed in the study report along with justification for exclusion.

Any anomalous concentration values observed at predose will be identified and discussed in the CSR. Participants who experience emesis during the course of the study will be excluded from the PK summaries and statistical analysis if vomiting occurs at or before 2 times median T_{max} .

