3.4.2.3. Rationale for Evaluation of Higher Dose of GBT021601

As of Protocol Amendment 5, after a total of 8 weeks of treatment, all participants in this study demonstrated improvements in hematologic parameters, including reticulocytes and absolute reticulocytes, lactate dehydrogenase, and indirect bilirubin (Brown, 2021). Preliminary findings indicate a dose-related mean increase from about 15% to 32% in Hb occupancy after dosing with 50 mg daily and 100 mg daily respectively. Preliminary clinical safety data show that GBT021601 has been well tolerated with no significant treatment-related safety findings reported. An extended treatment period evaluating a dose escalation to 150 mg once daily for at least 6 weeks preceded by a loading dose of 300 mg, given twice daily over 4 days (the loading dose is being administered twice daily to minimize the potential for any gastrointestinal effect

that could theoretically occur with a higher once daily loading dose) is targeted to increase the Hb occupancy to approximately 54%. These projections were obtained from a population pharmacokinetic (PPK) model using the data from all 6 participants who have been enrolled in this study.

The Extended Treatment Period is being added to explore the safety and tolerability of these loading and maintenance dose levels. It is believed that higher Hb occupancy will translate to clinical benefits such as improved signs and symptoms of anemia, potentially reduced VOCs, and improved overall well-being in participants with SCD. To assess the full potential of this new agent, a formal multicenter dose-ranging study is being planned to evaluate higher doses of GBT021601, and it is critical to determine to safety/tolerability and effects on Hb occupancy and other hematological parameters at this proposed regimen (300 mg bid x 4 days plus 150 mg QD for 81 days).

CCI [REDACTED]

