7.5. Administration

GBT021601 will be administered orally. For the single-dose period, participants will fast at least 10 hours before and for at least 4 hours after study drug administration. Water will be allowed as desired except for 1 hour before and 1 hour after study drug administration.

For the multiple ascending-dose period of the study, GBT021601 can be taken with or without food.

Each dose will be administered orally with approximately 240 mL of water (additional water to complete dosing is allowed). Participants will be instructed to swallow the tablets or capsules within 5 minutes. If the participant vomits, the dose should not be repeated.

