6. PHARMACOKINETIC AND PHARMACODYNAMIC ANALYSIS

6.1 Pharmacokinetic Analysis

Pharmacokinetic variables will be calculated from the RBC, plasma and whole blood concentration data for GBT021601 using non-compartmental methods CCI [REDACTED] and actual sampling times for single dose part only.

The following PK parameters will be determined for RBC, plasma and whole blood concentrations of GBT021601:

Single-dose parameter:

Term	Parameter	Description
C_{\max}	Maximum observed concentration	Observed peak concentration obtained directly from the experimental data without interpolation.
t_{\max}	Time to maximum observed concentration	Time corresponding to C_{\max} .
AUC_{0-24}	AUC from time 0 to 24 hr	Calculated by linear/log trapezoid rule. At 24 hr the last quantifiable concentration
AUC_{0-t}	Area under the concentration-time curve (AUC) from time 0 to the time of the last quantifiable concentration	Calculated by linear/log trapezoid rule.
$AUC_{0-\infty}$	AUC from time 0 to infinity	$AUC_{0-t} +$ the area extrapolated from the last quantifiable concentration to infinity (i.e., C_{last}/λ_z).
CL/F Apparent Oral Clearance	Dose/ $AUC_{0-\infty}$	Dose/ $AUC_{0-\infty}$
V_z/F	Apparent volume of distribution	Dose/($AUC_{0-\infty} * \lambda_z$)
$t_{1/2}$	Terminal phase (apparent elimination) half-life	$\ln(2)/\lambda_z$

The concentrations of GBT021601 in RBC will be derived using the following equation:

$$RBC\ Conc = \frac{Blood\ Conc - [(1 - Hematocrit) * Plasma\ Conc]}{Hematocrit}$$

The RBC concentration will be determined using individual hematocrit data collected on the day of PK sample collection. If hematocrit data are not available, the RBC value will be set to missing.

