Only data points that describe the terminal elimination log-linear decline will be used in the regression equation for calculation of λ_z ; C_{max} and any data point in the distribution phase are not included in the calculation. A minimum of 3 points will be used for determination of λ_z . A general rule of adjusted $R^2 \geq 0.80$ will be considered as acceptable for calculation of λ_z . If adjusted R^2 falls below 0.80, then λ_z will be reported as Not Determined (ND) and that participant's values for λ_z , $t_{1/2}$, CL/F , V_z/F and $AUC_{0-\infty}$ will be reported in the appropriate listings but will be flagged and excluded from descriptive summaries and statistical analysis. If the extrapolated AUC_{inf} is more than 20%, then AUC_{inf} , CL/F and V_z/F will be listed but flagged and excluded from descriptive summaries and statistical analysis.

Blood to plasma ratios and RBC to plasma ratios for C_{max} and AUC will also be determined.

Multiple Dosing Period

Concentrations of GBT021601 in whole blood, plasma, and RBC will be listed for apparent C_{min} (minimum concentration from predose to 4 hours postdose) and C_{max} (maximum concentration from predose to 4 hours postdose) for each subject by visit and dose level. Descriptive statistics [n, arithmetic mean, SD, coefficient of variation (CV) %, geometric mean, and geometric mean CV%] will be summarized. For Part C, concentration data till Week 2 will not be summarized.

%Hb Occupancy

For both the SAD and MAD portions of the study the C_{max} (SAD) and apparent C_{min} and C_{max} (MAD) values will be used to calculate Hb occupancy with the following equation.

$$\% \text{ Hb occupancy} = \frac{[GBT021601]_{RBC}}{MCHC}$$

MCHC = mean corpuscular hemoglobin concentration; the MCHC value on the day of PK sample collection will be used. If MCHC value is not available, the % Hb occupancy value will be set to missing.

The % Hb occupancy of GBT021601 will be listed and summarized for each visit by treatment group, including n, arithmetic mean, SD, CV %, and in graphical format (linear scale [MAD only]).

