7.16 Pharmacokinetic Analysis

The PK population will be used for all concentration listings and individual figures. Plasma, RBC (if applicable) and whole blood GBT021601 concentrations will be listed and summarized for each visit/ time point for single dose including n, nBLQ, mean, SD, geometric mean, coefficient of variation (CV), median, minimum and maximum.

The drug concentrations will be presented in graphical formats (linear and semi-log scales) as mean and individual profiles. Overlay of individual RBC, plasma and whole blood GBT021601 concentration profiles over time will be provided.

All plasma, RBC (if applicable) and whole blood GBT021601 PK parameters for single dose will be listed for PK population. Summary statistics (n, mean, SD, geometric mean, median, minimum, maximum, and CV) will be calculated for the plasma, RBC and whole blood GBT021601 PK parameters. For t_{max}, only n, minimum, median and maximum will be reported.

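### SAP 6.2 applies a single-dose emesis exclusion to whole participants across the study; limit it to the Part A profile and, in Parts B and C, to affected visits

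*SAP*

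**What the plan says.** SAP 6.2 closes with a mandatory rule: "Participants who experience emesis during the course of the study will be excluded from the PK summaries". The same sentence bars them from the statistical analysis too. Its timing test is "if vomiting occurs at or before 2 times median" tmax. The unit is the participant and the stated span is the study. The paragraph before it works differently. There, an individual treatment profile may be excluded after review and discussion, and results with and without it may be shown.

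SAP 6.1 runs the analysis that yields tmax, on RBC, plasma and whole blood concentrations, with non-compartmental methods "and actual sampling times for single dose part only". For multiple dosing it lists apparent Cmin and Cmax, both taken from predose to 4 hours, "for each subject by visit and dose level", and defines no tmax. % Hb occupancy is computed from these values. Part C concentrations up to Week 2 are not summarized.

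SAP 7.1 analyses Parts A, B and C separately. SAP 7.16 keeps the listings complete: "All plasma, RBC (if applicable) and whole blood GBT021601 PK parameters for single dose will be listed for PK population". Protocol 7.5 adds: "If the participant vomits, the dose should not be repeated".

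**The concern.** After a single dose, vomiting before absorption is complete can remove most of the exposure, so dropping that profile is sensible. Under repeated dosing a vomited dose is one of many, and the data it can affect are limited to samples taken after it. The rule as worded does not make that distinction.

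It also cannot be programmed for Parts B and C without further choices. The SAP does not say after which dose the time is counted, which matrix supplies the median, or what median applies where no tmax is derived. In an open-label study those choices would be made with the data in view.

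PK is a secondary objective, SAP 3.5 relies on six participants to characterize it, and occupancy at the Part C regimen is among the things Part C was added to assess. A whole-participant exclusion would discard usable data. It would do so in people who vomited, so the remaining summary would lean towards those who tolerated the drug.

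**Working it through.** **What needs no pharmacokinetic assumption.** Part A precedes Part B by a washout of at least 56 days, so vomiting in Part B or C cannot alter a Part A profile. A visit before the episode cannot be altered, nor can a predose sample drawn before the vomited dose. The literal rule removes all three from the summaries. With six participants the loss is 1/6 = 16.7%.

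**Size of one lost dose.** The documents give no figure for this, so there is none to reproduce.

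Inputs:
- Part B (Protocol 3.3.2, days from Table 3): 300 mg on Day 56, 200 mg on Day 57, 50 mg/day to Day 90; 500 mg on Day 91, 400 mg on Day 92, 100 mg/day to Day 112.
- Part C (Protocol 4.3.3): 300 mg twice daily for 4 days, then 150 mg/day to Day 42.
- Half-life: none is reported. The anticipated cap is 120/5 = 24 days (Protocol 4.3.2). The Day 218 visit, about 5 half-lives after Day 112, implies (218 − 112)/5 = 21.2 days.

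Assumptions: one compartment, linear kinetics, immediate absorption, complete loss of the vomited dose. Carry-over between parts is ignored, which makes the shifts slightly too large.

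Formula: with k = ln 2 / half-life, losing dose m on day d lowers the predose amount at day t by m·exp(−k(t − d)) divided by the sum of m_j·exp(−k(t − d_j)) over all doses before t.

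Worked at 21.2 days, k = 0.0327:
- Part B Week 9 (Day 63): 238.6 mg remains from the 300 mg dose, 164.4 mg from the 200 mg dose and 226.9 mg from five 50 mg doses, total 629.9 mg. Losing the 300 mg dose costs 238.6/629.9 = 37.9%. Losing the 50 mg dose of the day before (48.4 mg remaining) costs 7.7%.
- Part C Week 6 (Day 42): 665.6 mg remains from loading and 3,167.0 mg from maintenance, total 3,832.6 mg. Losing the first 300 mg dose costs 78.5/3,832.6 = 2.0%. Losing the 150 mg dose of the day before costs 145.2/3,832.6 = 3.8%.

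The same formula gives, for predose amounts:

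| Dose lost | Visit | Half-life 24 d | Half-life 21.2 d |
|---|---|---|---|
| Part B 300 mg, Day 56 | Weeks 9 / 10 / 12 / 13 | 38.1 / 23.9 / 11.9 / 8.9% | 37.9 / 23.5 / 11.3 / 8.3% |
| Part B 500 mg, Day 91 | Weeks 14 / 15 / 16 | 18.5 / 13.7 / 10.4% | 19.0 / 13.8 / 10.3% |
| Part B 50 mg, day before | Weeks 9 / 10 | 7.6 / 5.8% | 7.7 / 6.0% |
| Part B 50 mg, day before | Weeks 12 / 13 | 4.3 / 3.9% | 4.5 / 4.2% |
| Part B 100 mg, day before | Week 16 | 3.7% | 4.0% |
| Part C first 300 mg dose | Weeks 4 / 6 | 3.8 / 2.2% | 3.6 / 2.0% |
| Part C 150 mg, day before | Weeks 4 / 6 | 4.0 / 3.5% | 4.2 / 3.8% |

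**Shorter half-lives.** At steady state on once-daily dosing, the shift just after one lost dose is 1 − exp(−k × 1 day): 2.8% at 24 days, 3.2% at 21.2, 6.7% at 10 and 12.9% at 5. A recent maintenance dose would then cost about 7–13% if the half-life were 5–10 days.

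**The case against.** **It is a Part A rule.** tmax exists only for Part A, multiple-dose results are summarized by visit, and the parts are analysed separately. A careful programmer might well apply the rule to Part A alone, or part by part. That reading is reasonable, and loss of a Part A profile because of Part C vomiting is the worst case. But the sentence points to the whole study and nothing in 6.2 restricts it. If Part A was meant, saying so takes a few words.

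**One lost dose is always trivial under repeated dosing.** A reader might infer this, and the table does not support it. Part B loading doses shift later visits substantially, and the small figures elsewhere rest on an assumed half-life. So keeping every Part B and C visit unflagged would also be wrong.

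**Data are lost or dosing decisions distorted.** Neither follows. Listings and individual figures keep the PK population. Escalation rested on committee review (Protocol 5.6 and 5.7), and the Part C regimen on a population model using all six participants (Protocol 3.4.2.3). The rule governs descriptive report summaries, with no formal tests.

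**Exclusion would be frequent and driven by dose.** The documents give no vomiting rate, so no probability of exclusion can be supported. Protocol 3.4.2.3 says only that "the loading dose is being administered twice daily to minimize the potential for any gastrointestinal effect", and it treats that effect as theoretical. Part C data up to Week 2, which cover the loading days, are not summarized anyway. Selection by tolerability is a possibility, not something shown.

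**Conclusion.** The concern holds in a bounded form. Applied as written, SAP 6.2 removes a participant from all PK and occupancy summaries for one episode near one dose, at a cost of 1 in about 6 and with data that the episode could not have touched. That part rests on the text alone.

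How much a lost dose matters to later samples varies by dose. At the 21–24 day half-life implied by the documents' planning figures, it is about 2–4% at Part C Week 6 for a loading or recent maintenance dose, and up to about 4–5% for late Part B maintenance doses. It is about 6–8% for early Part B maintenance doses. For the first dose of each Part B load it is about 10–38% at later visits, falling to 8–9% by Week 13 for the Day 56 dose. These figures assume simple linear kinetics and total loss of the dose. Even the largest justify setting aside the affected visits, not the participant's other data.

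**What to change.** In SAP 6.2:
- Limit the exclusion at twice median tmax to the Part A single-dose profile, using the tmax of the matrix being summarized.
- For Parts B and C, exclude by affected visit and not by participant. Always keep Part A data, visits before the episode, and the predose sample of the visit at which the dose was vomited.
- Flag that visit's postdose values and carry the flag to the apparent Cmax and occupancy derived from them. After a vomited loading dose, also flag the later visits at that dose level.
- Present the summaries with and without flagged visits, and list emesis episodes with dose times.

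The cost is a few sentences and one programming flag. AE onset date and time and dosing times are already planned for collection, so no new data are needed. The downside is that some modestly reduced exposures enter the main summary; the comparison with and without flagged visits shows the effect of those that are flagged. Nothing here bears on dosing after emesis.

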6.3 Non-Quantifiable Concentrations

All concentration values reported as no results (not collected or ND) will be treated as missing. For the calculation of concentration summaries, plotting mean and individual concentration time profiles, all concentrations below quantifiable limit (BLQ) will be treated as zero. For the purpose of calculating PK parameters, BLQ values will be treated as zero prior to the first measurable concentration. After the first measurable concentration, subsequent BLQ values will be treated as missing.

6.4 Pharmacodynamic Analysis

CCI

A separate report will be prepared for rest of the PD parameters analysis (hemoximetry and RBC deformability).

7.2 Handling of Dropouts or Missing Data

Missing data will not be imputed except for the way described to handle concentration in [Section 6.1.2](#).

7.3 Handling of missing/ incomplete dates for Adverse Event

Imputation rules for missing or partial AE start date are defined below:

If only Day of AE start date is missing:

If the start date has month and year but day is missing, the first day of the month will be imputed

- If this date is earlier than the first dose date, then the first dose date will be used instead.
- If this date is later than the stop date (possibly imputed), then the stop date will be used instead.

If Day and Month of AE start date are missing:

If the start date has year, but day and month are missing, the 1st of January will be imputed

- If this date is earlier than the first dose date, then the first dose date will be used instead.
- If this date is later than the stop date (possibly imputed), then the stop date will be used instead.

If Year of AE start date is missing:

If the year of AE start is missing or AE start date is completely missing, then imputation will not be done.

If the AE end date (full or partial) is before the first dose date then the AE should be considered as a pre-treatment AE. Otherwise, the AE will be considered as TEAE.

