^k Samples for PK will be collected: predose, 0.25 to 21 hours postdose and 2 to 4 hours postdose. Sample collection times for hemoximetry and RBC deformability should be aligned with the predose PK sample and the 2 to 4 hour postdose PK sample. No 0.25 to 1 hour postdose sample shall be collected for hemoximetry or RBC deformability. The predose blood sample for PK and PD assessments should be collected within 30 minutes prior to dosing.

Table 3-4: Schedule of Assessments for Extended Treatment Period (Part C)

Study Day/Week	Part C Screening Visit (Day -28 to Day -1)	Part C Day 1	Part C Week 2 (Day 14 ± 3 days)	Part C Week 4 (Day 28 ± 3 days)	Part C Week 6 (Day 42) ± 3 days) EOET	Part C Week 10 (Day 70 ± 3 days)	Part C Week 14 (Day 98 ± 3 days)	Final Visit (EOS/OLE)
Informed Consent	X							
Eligibility confirmation ^a	X							
Physical	X				X		X	X
Weight	X	X			X		X	X
Vital signs ^b	X	X	X	X	X	X	X	X
12-lead ECG (triple tracing) ^c	X	X	X	X	X		X	X
Study drug administration ^d		X	X	X	X			
Dispense participant diary ^e		X	X	X				
Collect participant			X	X	X			
CCl	█	█	█	█	█	█		
ly			█	█	█	█	█	█
and serum chemistry	X	X	X	X	X	X	X	X
Serum	X	X			X		X	X
eGFR ^f	X	X			X		X	X
Urinalysis	X	X			X		X	X
Pregnancy test (women only) ^g	X	X			X		X	X
Pharmacokinetic assessment		X	X	X	X	X	X	X
Hemoximetry ^h		X		X	X		X	X
RBC deformability, dense cells (if feasible) ^h		X		X	X		X	X
Blood smear		X			X		X	X
Concomitant medications		█			█			
Adverse events		X	X	X	X	X	X	X

Abbreviations: **CCI** ECG, electrocardiogram; eGFR, estimated glomerular filtration rate; EOET, End of Extended Treatment; EOS, end of study; ET, early termination; **CCI**

Note: For procedures scheduled to be performed at the same time, priority is to be given to collection of the PK samples at the designated time. ECGs, followed by vital signs, are to be taken before PK sampling unless PK samples will be late as a result.

^a For newly enrolled participants, the Screening Visit will be the same as that in [Table 3-1](#).

^b HR, BP, RR, and body temperature will be measured after a participant has rested for at least 5 minutes in the supine position. Assessment of vital signs may be performed up to 3 hours predose.

^c 12-Lead ECG should be performed within 30 minutes prior to dose at Part C Day 1, Part C Week 2, and 4 hours post dose at Part C Weeks 4 and 6. All ECGs will be collected in triplicate within 5 minutes after a participant has rested at least 5 minutes in the supine position.

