3.3 Evaluations at Screening and Check-in

Screening procedures will be conducted within 30 days prior to Day 1 dosing (Day -30 to Day -2). Screening and check-in evaluations for the single dose period each period are presented in [Table 3-1](#) and screening activities for Part C are found in [Table 3-4](#).

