3.12 Evaluation of Treatment Safety

3.12.1 Adverse Events

An adverse event (AE) is defined as any untoward medical occurrence associated with the use of a drug in humans, whether or not considered related to the study drug. An AE can therefore be any unfavorable and unintended sign, symptom, or disease temporally associated with the use of a study drug. A suspected adverse reaction is any AE for which there is a reasonable possibility that the drug caused the AE.

A treatment-emergent AE (TEAE) is an AE that occurs or worsens during the on-treatment period defined as the time from the first dose of study drug through minimum of 56 days + last dose of study treatment, date of study completion/discontinuation.

A Serious Adverse Event (SAE) is defined as any event that results in death, is immediately life threatening, requires inpatient hospitalization or prolongation of existing hospitalization, results in persistent or significant disability/incapacity, or is a congenital anomaly/birth defect or important medical events.

All AEs will be recorded from the time the study participant signs the Informed Consent Form (ICF) until the EOS Visit or ET Visit, whichever comes first. All AEs must be reported on the AE electronic case report form (eCRF) via the electronic data capture system. All serious and non-serious AEs must be followed until they are resolved or stabilized, or until reasonable attempts to determine resolution of the event are exhausted. Any participant who experiences an AE may be discontinued from study treatment at any time at the discretion of the Investigator. The Sponsor/Medical Monitor(s) must be notified of the study participant discontinuation.

The following details will be collected: description of the AE, onset date/time, action taken with study drug, outcome, severity (grade 1, grade 2, grade 3, grade 4 or grade 5), seriousness (yes, no) and relationship to study drug administration (not related or related).

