7.4 Handling of missing or partial Prior/Concomitant Medication Dates

Missing or partial medication start date:

- a. If only Day is missing, the first day of the month will be assumed.
- b. If Day and Month are both missing, the first day of the year will be assumed.
- c. If Day, Month and Year are all missing, the day before the first dose date will be assumed.

Missing or partial medication stop date:

- a. If only Day is missing, the last day of the month will be assumed.
- b. If Day and Month are both missing, the last day of the year will be assumed.
- c. If Day, Month and year are all missing, ‘ongoing status to stop date will be assigned.

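### SAP 7.3 moves a partly dated AE to the first dose date even when its recorded month or year shows it began earlier, so some pre-dose AEs are counted as TEAEs

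*SAP*

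**What the plan says.** SAP 7.3 handles partial AE start dates in two parallel branches. If only the day is missing, the first of the recorded month is imputed. If day and month are missing, 1 January of the recorded year is imputed. Both branches carry the same override: "If this date is earlier than the first dose date, then the first dose date will be used instead". Both then cap the start at the stop date. If the year is missing, nothing is imputed.

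The section closes with a classification rule: "If the AE end date (full or partial) is before the first dose date then the AE should be considered as a pre-treatment AE", followed by "Otherwise, the AE will be considered as TEAE".

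The definition is in SAP 3.12.1, where a TEAE "is an AE that occurs or worsens during the on-treatment period defined as the time from the first dose of study drug". The same section starts AE collection earlier: "All AEs will be recorded from the time the study participant signs the Informed Consent Form (ICF) until the EOS Visit or ET Visit". SAP 3.3 gives the length of the pre-dose window: "Screening procedures will be conducted within 30 days prior to Day 1 dosing (Day -30 to Day -2"). Under SAP 7.17.1 the AE summaries are built on TEAEs.

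**The concern.** Using the first dose date is a sensible convention when the recorded parts leave the order of onset and dosing open. An AE recorded as March, in a participant dosed on 10 March, could have begun on either side of the dose. The rule in SAP 7.3 does not stop there. It also fires when the recorded month or year lies wholly before the first dose. In that case the order is known and the imputation overwrites recorded information.

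Because AEs are collected from consent and screening can start 30 days before dosing, the pre-dose period often crosses a month boundary, so such records can arise. They arise in Part A, and also in Part C for anyone whose first study dose is there (footnote a of SAP Table 3-4 provides for newly enrolled participants).

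Safety and tolerability form the primary objective, and the study plans for about six participants. A single misclassified AE can therefore visibly change an incidence.

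**Working it through.** **Inputs.** The imputation, override, stop-date cap and closing rule are from SAP 7.3. The TEAE definition and start of AE collection are from SAP 3.12.1. The screening window is from SAP 3.3, and the six participants are from SAP 3.5. The documents give no figure on this point, so there is none to reproduce. The first dose date below is an assumption for illustration.

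**Step 1: apply the rule literally.** Assume first dose on 10 March 2021.

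| Recorded start | End | Start under SAP 7.3 | Class under SAP 7.3 | Class if known parts are respected |
|---|---|---|---|---|
| Feb 2021 | ongoing | 10 Mar 2021 | TEAE | pre-treatment |
| Feb 2021 | 15 Mar 2021 | 10 Mar 2021 | TEAE | pre-treatment |
| 2020 | ongoing | 10 Mar 2021 | TEAE | pre-treatment |
| Mar 2021 | ongoing | 10 Mar 2021 | TEAE | TEAE |
| 2021 | ongoing | 10 Mar 2021 | TEAE | TEAE |
| Feb 2021 | 5 Mar 2021 | 5 Mar 2021 | pre-treatment | pre-treatment |

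The first three rows are the defect. The next two are ambiguous and handled reasonably. The last shows that AEs ending before first dose are already classified correctly.

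For comparison, an ongoing AE fully dated 28 February 2021 is pre-treatment under SAP 3.12.1 unless it worsens. The same AE with the day missing becomes a TEAE, although both records prove onset before 10 March.

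The medication rule has no override: "If only Day is missing, the first day of the month will be assumed". A drug started in February 2021 for that AE would be dated 1 February, 28 + 9 = 37 days before the imputed onset of the event it treats. Medications are only listed, so this affects coherence and no summary.

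**Step 2: how often the month alone settles the order.** Let p(j) be the share of first-dose dates in a calendar year for which the day j days earlier falls in an earlier month. Over the 365 possible first-dose dates of 2021 and j = 1 to 30, there are 365 × 30 = 10,950 pairs. Of these, 5,577 fall in an earlier month: 5,577 / 10,950 = 50.9%. Over a 7-day window the share is 336 / 2,555 = 13.2%. For year-only records over 30 days it is 465 / 10,950 = 4.2%.

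**Step 3: restrict to AEs unresolved at first dose.** The shares in step 2 cover every pre-dose onset, while the rule changes only those still open at dosing. Assume onset uniform over the 30 days and exponential duration with mean m days, so the chance of being unresolved j days after onset is S(j) = exp(−j/m). Then:

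- share provably earlier, among unresolved AEs = Σ p(j)S(j) / Σ S(j)
- share both provably earlier and unresolved, among all day-missing pre-dose AEs = Σ p(j)S(j) / 30

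| Assumed mean duration m | Provably earlier, among unresolved | Both, among all |
|---|---|---|
| 3 days | 12% | 1% |
| 5 days | 18% | 3% |
| 7 days | 23% | 5% |
| 14 days | 35% | 14% |

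Unresolved AEs cluster close to dosing, where the month is less likely to differ, so these shares are below 51%.

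**Step 4: weight of one participant.** 1/6 = 16.7 percentage points.

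**The case against.** The strongest reply is that the rule is conservative: it can add events to the TEAE count but cannot remove any. It also has little to act on. AEs are assessed at Screening, on Day -1 and through confinement, onset date and time is a collected field, and queries and edit checks run under the data management plan. Few AEs should have partial dates, and a year-only onset within a 30-day window is remote. All of this stands and limits the size. It does not defend the rule where the order is known, because no uncertainty is then left to be conservative about.

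A second reply concerns the remedy. The AE fields listed in SAP 3.12.1 include an onset and a severity but no date of worsening. Moving such AEs to pre-treatment could lose one that worsened on treatment. Protocol 10.1.1 largely answers this, since it makes any increase in severity or frequency of a pre-existing condition after consent an AE in its own right. The residual risk is a worsening that was never recorded, and the fix must cover it.

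A reader might also infer that the closing sentences of SAP 7.3 make TEAE status depend on the end date alone for every AE, even fully dated ones. The text does not settle that. Those sentences directly follow the missing-year branch and may govern only AEs with no start year, where the end date is all there is. If they cover all partly dated AEs, they give the same misclassification by a second route. The defect does not depend on this, because the override alone moves the onset to first dose.

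**Conclusion.** The point holds as a minor error in a stated rule. SAP 7.3 discards a recorded month or year that proves onset before dosing, and the resulting classification conflicts with SAP 3.12.1. No other part of either document limits the override.

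It concerns only AEs that are partly dated, recorded between consent and first dose, provably earlier by month or year, and not ended before first dose. The documents give no count, and it may be zero. The 1% to 14% range rests on the assumed durations, uniform onset and a 30-day window. The error runs toward more TEAEs, no test is involved, and the AE listings remain available.

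Two larger readings should not be drawn. The 51% figure is not the share misclassified, since most short AEs from early in the window would have ended before dosing. Nor do the documents support a separate override at the start of each part: the SAP speaks of the first dose of study drug in the TEAE definition, the study-day formula (7.1) and the medication definitions (7.17.5).

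**What to change.** In SAP 7.3:

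- Substitute the first dose date only when the known date parts (month and year, or year alone) equal those of the first dose.
- If the known parts are earlier, keep the AE as pre-treatment unless a worsening on or after first dose is recorded.
- State that the closing sentences apply only when the known start parts do not already settle the order, and that ambiguous AEs remain TEAEs.

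The cost is one added condition and a clarification of the closing sentences. The downside is that a worsening not entered as a new or updated AE could be missed. To guard against that, list every partly dated AE reclassified as pre-treatment for medical review before database lock.
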